11.2.2. Analysis of secondary endpoints

- Per-protocol analysis of sensitivities and specificities of Ultra on stool using TB culture reference standard (LJ ans MGIT) in respiratory sample, excluding invalid Ultra results, contaminated and NTM culture results from analysis. Regarding contamination, since two culture methods will be used per respiratory sample (LJ and MGIT), to be excluded both culture results per sample will need to be contaminated.
- Head to head comparison of the sensitivities and specificities between the different stool processing methods using culture reference standard and McNemar test for matched data:
 - Sucrose flotation classic method vs Sucrose Flotation optimised method
 - Sucrose flotation classic method vs SPK method
 - Sucrose flotation classic method vs STEP method
 - Sucrose flotation optimised method vs SPK method
 - Sucrose flotation optimised method vs STEP method
 - SPK method vs STEP method
- Head to head comparison of the sensitivities and specificities between the different stool processing methods using the TB composite reference standard as defined by Clinical Case Definition for Classification of Intrathoracic Tuberculosis in Children, and McNemar test for matched data:
 - Sucrose flotation classic method vs Sucrose Flotation optimised method
 - Sucrose flotation classic method vs SPK method
 - Sucrose flotation classic method vs STEP method
 - Sucrose flotation optimised method vs SPK method
 - Sucrose flotation optimised method vs STEP method
 - SPK method vs STEP method
- Description of results for rifampicin resistance using stool Ultra, respiratory Ultra, LPA and DST
- Agreement of the different stool sample processing methods for Ultra detection head to head using Kappa analysis.
- Comparison of the proportion of rifampicin resistance indeterminate Ultra test results between different stool processing methods using McNemar test for matched data.
- Comparison of the proportion of invalid Ultra test results between different stool processing methods using McNemar test for matched data.
- Comparison of the proportion of Ultra results "trace" between the methods using McNemar test for matched data.
- Proportion of very low, low, medium and high Xpert Ultra results by different methods

- Change in sensitivity and specificity at patient level by using 2 stools vs using just the 1st stool specimen for each processing method.
- Stratification of children's characteristics and laboratory results by age groups (<2, 2 to 5, 5 to 10, and >10 years))
- Proportion of children successfully providing a stool sample
- Relative gain of Ultra MTB detection by using ratio of TB detected using 2 stools vs using just the 1st stool specimen for each processing method.
- Description of the results of the ease of use questionnaire for feasibility by technician and time of assessment (beginning, half way and end of the study).

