methods. However, it is difficult to know which method has the best accuracy and potential for use at PHC level, due to the difference in study designs and populations. Therefore, in this study, we propose to evaluate the accuracy of different promising stool processing methods in the same population within the same study with an adapted design. Furthermore, no study has so far evaluated for stool testing the new Xpert MTB/RIF Ultra cartridge that has a lower level of detection than the previous Xpert MTB/RIF cartridge. We propose to evaluate the accuracy of Xpert MTB/RIF Ultra (Ultra) performed on stool samples collected from children with presumptive TB and processed using four different processing methods (Standard sucrose flotation method, optimized sucrose flotation method, SPK, and STEP) against bacteriological results from respiratory specimens and to perform a head-to-head comparison of the diagnostic accuracy and feasibility of these different methods in Uganda and Zambia. The selection of processing methods was based on accuracy results, degree of simplification allowing their introduction at PHC level, and finding from the TB-Speed in-vitro stool processing study. The standard sucrose flotation method is kept to assess if results obtained with the optimised sucrose-flotation method in our in-vitro study can be reproduced in-vivo.

Participating countries

The study will take place in Zambia and Uganda, both countries participating already in other TB-Speed studies. Zambia is among the 30 high TB burden countries according to the WHO classification with a TB incidence rate of 361/100 000 population, while Uganda is in the top 20 high TB/HIV burden countries with a TB incidence rate of 201/100,000population.

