4.3. Sample size

As we want to estimate two proportions, specificity and sensitivity, we need to ensure a sufficient sample size for these two estimates.

The first stage is to estimate specificity by enrolling children with presumptive TB. With an expected specificity of Ultra in stool of 90%, the minimum sample size to estimate specificity with 5% precision, is 140 children with presumptive TB and negative TB culture from two respiratory samples. Inflating this number by 15% for attrition (to a total of 160 children) and considering a 10% prevalence of culture-confirmed TB in our population, we will need to enrol a total of 177 children with presumptive TB.

The second stage is to estimate sensitivity among presumptive TB children with culture confirmed TB. With an expected sensitivity of Ultra in stool of 60%, based on a literature review, the minimum sample size to estimate sensitivity with 10% precision, is 93 children with culture-confirmed TB. Inflating this number by 10% for attrition and invalid results, we will need a total of 103 confirmed TB cases. We expect 16 culture confirmed to be enrolled during the first stage (10% of 160 children enrolled in the prospective cohort). Then we will need to enrol an additional 87 children during the 2nd stage from presumptive TB children with a respiratory sample positive with Xpert Ultra (enrichment cohort). Knowing that only 90% of these children will ultimately be culture positive, we will need to further inflate the number of children to be recruited based on Ultra result in their respiratory sample [84]. We will therefore a total of enrol 97 children with Xpert Ultra positive results during the second stage.

Given routine site data and estimated enrolment figures for the Ugandan and Zambian study site, we expect to enrol children for the first stage in approximately 12 months, and Ultra-positive children for the second stage in 11 months.

For the secondary endpoints, in order to test Kappa coefficients with a minimum acceptable value of 0.4 [47], considering the study sample size, we will be able to detect a minimum change of 0.1 in Kappa coefficient between the stool sample processing methods with 80% power.

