11.2. Description of the statistical analysis plan

11.2.1. Analysis of the primary endpoint

Sensitivity of the 4 Ultra on stool using TB culture reference standard (LJ and MGIT) in respiratory sample: point estimate and 95% CIs.

Specificity of the 4 Ultra on stool using TB culture reference standard (LJ and MGIT) in respiratory sample: point estimate and 95% CIs.

We will use as TB culture reference standard:

- Positive: at least one positive MTB culture result in one of the two respiratory samples
- Negative: negative culture results from 2 samples without any positive result

An intention-to-diagnose analysis will be performed at:

- Sample level (denominator: total number of samples collected): 1 stool vs the TB culture reference standard
- Patient level (denominator total number of cases with at least one stool sample collected): at least 1 of the two stools vs the TB culture reference standard.

A patient will be classified as stool positive, when they have at least one positive stool Ultra result (for example the first stool may not have any positive Ultra results, but the second stool could have 1 positive Ultra result, in which case the patient would be considered stool positive).

Invalid Ultra results, contaminated and NTM culture results will be considered negative.

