19.2. APPENDIX 2: in-vitro study summary

Development of a simple sample processing method for diagnosis of intrathoracic pediatric tuberculosis using Xpert Ultra testing of stool- results of an *in vitro* study.

[name], [name], [name], [name], [name], [name], [name] and [name]

Background

Stool samples are promising alternatives to respiratory samples for molecular diagnosis of childhood tuberculosis (TB) but they require intensive laboratory processing before molecular testing to remove PCR inhibitors and debris. We aimed to develop a centrifuge-free stool processing method for use at peripheral level in resource-limited settings.

Method

In an *in vitro* laboratory study, we tested alternative parameters to optimize a sucrose-flotation method using centrifugation, filtration and vortex shaking that previously showed good sensitivity for childhood TB diagnosis when combined with Xpert: modified amount of stool, manual shaking, no filtration, sedimentation vs centrifugation, modified dilution ratio. Each alternative parameter was compared head-to-head with the reference method using Xpert MTB/RIF Ultra (Ultra) on stool samples spiked with $10^3 M$. *tuberculosis* colony forming units (CFU)/g. We selected the best index methods using a drop-the-loser rule: after 15 tests, methods with invalid/errors > 20% (maximum threshold) were dropped; after 30 tests methods with invalid/errors < 20% and a sensitivity difference with the reference method <10% were kept. For final selection, we tested the best parameters combinations at 10^2 CFU/g. We also assessed methods in terms of quantitative Ultra results (cycle thresholds (CTs)) for MTB detection.

Results

Out of 13 different combinations three were tested at 10^2 CFU/g (Table). The best combination used 0.5g stool, manual shaking, no filtration, 30-minutes sedimentation, and a 1:5 dilution ratio. It had 10% invalid/error results and a sensitivity of 70% (95% CI 50.4-84.5) and 53% (38.8-78.1) vs 63% (43.9-79.4) and 58% (40.7-79.1) as compared to the reference method, at 10^3 and 10^2 CFU/g, respectively.

Discussion

We identified an optimized centrifuge and vortex-free stool sample processing method with potential to facilitate stool Xpert Ultra testing in high burden and resource-limited settings. It should be further evaluated among children with presumptive TB.

Table:

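### The head-to-head accuracy comparisons name only McNemar tests, so the plan gives no interval for how much accuracy a simplified method may lose

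*Protocol*

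**What the plan says.** Section 11.2.1 asks for each method's sensitivity and specificity as "point estimate and 95% CIs". Section 11.2.2 then lists six pairs of methods and compares them "using culture reference standard and McNemar test for matched data". The same six pairs are repeated with the composite reference standard, again by McNemar. Kappa is planned for agreement between methods. No interval for a paired difference is named.

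Section 4.3 sizes the study on single proportions. Taking 60% as the sensitivity, it states that "the minimum sample size to estimate sensitivity with 10% precision, is 93 children with culture-confirmed TB". After inflation the target is 103: "Inflating this number by 10% for attrition and invalid results, we will need a total of 103 confirmed TB cases". The only between-method power statement there concerns agreement: "we will be able to detect a minimum change of 0.1 in Kappa coefficient between the stool sample processing methods with 80% power".

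The Rationale in section 1 says that the standard flotation method is retained "to assess if results obtained with the optimised sucrose-flotation method in our in-vitro study can be reproduced in-vivo". In Appendix 2, the laboratory selection was made on the size of a difference: after 30 tests, methods with few invalid or error results and "a sensitivity difference with the reference method <10% were kept".

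**The concern.** Whether a simplified method reproduces the standard one is a question about the size of a difference and its uncertainty. A test of no difference answers another question: whether the data are incompatible with exactly zero. If the test is significant, the reader still needs the range of the difference. If it is not, the reader cannot tell close agreement from too few discordant pairs.

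The protocol asks for an estimate with an interval where it describes a single method, but for a test alone where it compares methods. The comparison matters here. Section 4.1 accepts that enrolling Xpert-positive children may inflate sensitivity, and points to the variation between methods as the information that remains valuable. Users choosing a centrifuge-free method would want to know how large a loss the data leave open.

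**Working it through.** **1. The plan's own figure.** For a single proportion with p = 0.60 and half-width 0.10:

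n = 1.96² × 0.60 × 0.40 / 0.10² = 92.2, rounded up to 93.

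Then 93 × 1.10 = 102.3, rounded up to 103. Both figures in section 4.3 reproduce. They concern the interval around one method's sensitivity, not the difference between two methods tested in the same children.

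**2. Inputs for the paired comparison.**
- n = 93 or 103 culture-confirmed children (section 4.3), analysed at patient level.
- Two-sided 5% test: assumed, as no alpha is stated for McNemar.
- Share of discordant pairs: assumed at 15%, 20% and 30%, as the protocol gives none.
- True loss of 10 points: an illustrative value, not a margin.

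As a rough anchor for discordance, suppose both methods have 60% sensitivity. Chance agreement among confirmed cases is 0.60² + 0.40² = 0.52, so discordance = 0.48 × (1 − kappa). The minimum acceptable kappa of 0.4 in section 4.3 gives 28.8%; kappa 0.6 gives 19.2% and kappa 0.8 gives 9.6%.

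**3. Power of McNemar.** With discordance D and difference 0.10, the two discordant cells have probabilities (D + 0.10)/2 and (D − 0.10)/2. The number of discordant pairs is binomial(n, D). Given m discordant pairs, the split is binomial with probability (D + 0.10)/(2D). Summing the rejection probability over m gives:

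| Discordance | 93 cases, asymptotic | 93 cases, exact | 103 cases, asymptotic | 103 cases, exact |
|---|---|---|---|---|
| 15% | 73.7% | 65.3% | 78.6% | 71.2% |
| 20% | 60.4% | 51.0% | 65.3% | 55.9% |
| 30% | 43.5% | 34.5% | 46.9% | 38.5% |

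**4. Width of the interval the plan omits.** The Wald half-width for a paired difference of 0.10 is 1.96 × √((D − 0.10²)/n). With n = 93:
- D = 0.15: 1.96 × √(0.14/93) = 7.6 points
- D = 0.20: 1.96 × √(0.19/93) = 8.9 points
- D = 0.30: 1.96 × √(0.29/93) = 10.9 points

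**5. A worked table.** Take 93 confirmed cases with 28 discordant pairs (30%), of which 19 favour the standard method and 9 the simplified one.
- Exact McNemar p = 0.087. The asymptotic statistic is (19 − 9)²/28 = 3.57, p = 0.059. Neither is significant at 5%.
- Observed loss: 10/93 = 10.8 points.
- Standard error: √(28 − 10²/93)/93 = 0.0558. Wald 95% CI: 10.8 ± 10.9, or −0.2 to 21.7 points.

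McNemar alone would report no significant difference. The interval shows that the data also allow a loss of more than 20 points.

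**6. What the other planned analyses add.** Each paired difference can be obtained by subtracting two per-method estimates. Its interval cannot, because its variance depends on the discordant counts, which the separate per-method intervals do not contain. Kappa measures agreement, not the direction or size of a change in sensitivity.

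**The case against.** The case against has weight. McNemar suits matched binary data, and nothing in section 11.2.2 forbids an added interval. Section 11.1 says a statistical analysis plan will be written, and it could supply one. The comparison is secondary; the primary endpoint is accuracy per method. The sentence about reproducing laboratory results in vivo concerns one pair of the six. The size and direction of every difference can be read from the per-method estimates. All of this stands, and it limits the point to a reporting improvement. It does not remove it: the protocol specifies intervals for single methods and only a test for comparisons, which is a stated choice.

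Three stronger readings are tempting and not supported.
- A reader might infer that the protocol intends to treat a non-significant result as equivalence. No section says so; the stated aim is to compare.
- A reader might infer that a 10-point loss would probably be missed. With 93 cases the asymptotic test is more likely than not to detect it at 15% and 20% discordance, and the exact test does slightly better than even at 20%. A miss is the likelier outcome only at 30%. If discordance were near 10%, power would be above 90% with either test.
- A reader might take the 10% rule in Appendix 2 as a ready-made margin. It was a screening rule for dropping methods tested on spiked stool, not a clinical margin.

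**Conclusion.** The point holds as a limit on what the planned comparison can show, not as an error in the test. Section 11.2.2 provides no interval for any paired difference, and the other planned analyses do not fill the gap. A non-significant result at 93 to 103 confirmed cases can be compatible with a sensitivity loss of 10 points or more. Exact power against such a loss runs from 65% down to 35% with 93 cases, and from 71% down to 39% with 103, as discordance rises from 15% to 30%.

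These figures rest on assumed discordance, an assumed two-sided 5% test and patient-level pairs. The 10 points are illustrative. Power for specificity was not calculated; there the point is only that the same interval is missing. It is best classed as a cheap improvement.

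**What to change.** In section 11.2.2, for each of the six pairs and for both reference standards, make the paired difference in sensitivity and in specificity the main result, with a 95% CI for matched proportions (for example Tango or Newcombe paired). Keep the McNemar p-value as support. Add a sentence that a non-significant result is not evidence of equal accuracy. Do not adopt the Appendix 2 screening rule as a clinical margin.

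The cost is a little extra analysis from the same 2x2 tables. No further children, samples or tests are needed.

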3.3. Reference diagnosis/case definition for the study and validation by the Expert Committee

For the secondary endpoint of the evaluation of the accuracy of the Ultra test on stool against the TB composite reference standard, children will be classified into 3 categories, according to the updated Clinical Case Definitions for Classification of Intrathoracic Tuberculosis in Children, detailed in Table 2: *confirmed*, *unconfirmed*, or *unlikely* tuberculosis or any subsequent published update at the time of final case review if feasible and approved by the Scientific Advisory Board (SAB). Classification will be done by an expert committee set up for the TB-Speed HIV and TB-Speed SAM studies.

Case definition	Refined criteria
Confirmed tuberculosis	Bacteriological confirmation obtained (Mycobacterium tuberculosis confirmed by culture or Xpert MTB/RIF assay from at least 1 respiratory specimen)
	Bacteriological confirmation NOT obtained AND at least 2 of the following:
	 Symptoms/signs suggestive of tuberculosis¹
	CXR consistent with tuberculosis ²
Unconfirmed tuberculosis	Close tuberculosis exposure or immunologic evidence of M. tuberculosis infection
	 Positive response to tuberculosis treatment (requires documented positive clinical response on tuberculosis treatment—no time duration specified)
	AND no spontaneous improvement of symptoms in the absence of antituberculosis treatment
Unlikely	Bacteriological confirmation NOT obtained AND criteria for "unconfirmed tuberculosis" NOT met
tuberculosis	(including spontaneous improvement of symptoms in the absence of antituberculosis treatment)

Table 2. Updated Clinical Case Definition for Classification of Intrathoracic Tuberculosis in Children (adapted from Graham et al, 2015 [42])

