This two-stage sequential design first estimating specificity then sensitivity has been described by Wruck *et al.* [43] as an efficient way of validating diagnostic tests when the prevalence of the disease is low. It would not be feasible to consecutively enrol all children with presumptive TB to describe an expected sensitivity of 60% with 10% precision as this would require over 900 patients, of which, approximately 800 would be culture negative. In the two-stage process described by Wruck, only reference standard positive samples from the original population are selected in stage 2. We adapted this design to the TB context as culture results will only be available after enrolment (and if the child is positive, only after they have started treatment), hence selecting only those who are Ultra positive on respiratory samples for the second cohort as a way of enriching the study population with a subpopulation that has a higher TB prevalence probability, before their true disease status

is confirmed. Other comparable diagnostic studies have either used greater resources to include larger samples sizes (Dorman [14] and Wang [44]) or have resorted to reporting imprecise estimates of sensitivity [79-84]. To our knowledge, this is a relatively unique approach to study design for accuracy studies, with few published examples [45,46].

With such design, there should be no bias on the evaluation of the specificity similarly to a classical prospective design because this evaluation will be done among consecutively enrolled children with presumptive TB only. The sensitivity estimates may not be generalizable to all culture confirmed TB children due to the sampling approach. Xpert positive children will be more likely to have higher biological loads, causing a possible inflation of the sensitivity. However, the results will provide valuable information on variations of sensitivities of the different stool processing methods within this population.

We will carry out an interim analysis after the completion of the prospective cohort in order to describe specificity and preliminary results of the sensitivity and the agreement between the processing methods. The recruitment of participants will not be put on hold during the interim analysis. We will conduct a final analysis at the end of the study to describe sensitivity as well as the secondary end points.

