4.2. Methodology

Enrolment will have 2 stages. During stage 1 (prospective cohort stage), all consecutive children with presumptive TB enrolled in the TB-Speed HIV or TB-Speed SAM or seen in routine care if ineligible for those two studies will be proposed to participate in the study until we reach the number needed for the evaluation of specificity. All children with presumptive TB will have at least two respiratory samples collected (ES or GA) tested with Ultra and mycobacterial culture. The cohort will be closed once the sample size of presumptive TB children with two negative Ultra results from respiratory samples will be reached.

During the 2nd phase (enrichment phase), only children with presumptive TB who are Xpert positive on at least one respiratory sample will be proposed to participate in the study in order to complement the number of confirmed TB cases required for the evaluation of the sensitivity.

TB-Speed SAM and HIV studies

TB–Speed SAM is a multicentric prospective diagnostic cohort study aiming to assess several diagnostic tests that could result in the development of a score and algorithm for TB treatment decision in hospitalised children with severe acute malnutrition (SAM). It will enrol 720 children <5 years old with WHO-defined severe acute malnutrition in Uganda and Zambia.

TB-Speed HIV is a Prospective, multicentre management study evaluating the safety and feasibility of the recently proposed PAANTHER TB treatment decision algorithm for HIV-infected children with presumptive TB. 550 HIV-infected children aged <15 years with clinically suspected (presumptive) TB will be enrolled from Côte d'Ivoire, Uganda, Mozambique and Zambia.

Prospective cohort:

Any child with presumptive TB will be proposed to participate in the study.

If the child is enrolled in the TB Speed SAM or HIV studies, the study nurse will collect two stool samples then collect information about the clinical examination, chest X-ray, HIV-testing and the mycobacterial culture results as soon as they are available, from the data collected in the TB-Speed records since all these procedures are already performed in these studies.

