 as preliminary results of the sensitivity and the agreement between the processing methods.
- A final analysis will be conducted at the end of the study to describe sensitivity as well as the secondary end points.
- Follow-up: children will be followed up for 2 months upon enrolment, regardless of their TB diagnosis with protocol visits at day 1 and month 2.

Sample size: 274 children (below 15 years old)

- Inclusion criteria (prospective cohort):
- Children < 15 years of age
- Presumptive intra-thoracic TB based on at least one criterion among the following:
 - Persistent cough for more than 2 weeks
 - Persistent fever for more than 2 weeks
 - Recent failure to thrive (documented clear deviation from a previous growth trajectory in the last 3 months or Z score weight/age < 2)
 - o Failure of broad-spectrum antibiotics for treatment of pneumonia
 - Suggestive CXR features

OR

- History of contact with a TB case and any of the symptoms listed under point 2 with a shorter duration (< 2 weeks) if the child is HIV infected or present a SAM.
- Signed informed consent by parent or guardian and assent signed by children > 7 years old.

Inclusion criteria (enrichment cohort):

- Children < 15 years of age
 - Presumptive intra-thoracic TB based on at least one criterion among the following:
 - Persistent cough for more than 2 weeks
 - Persistent fever for more than 2 weeks
 - Recent failure to thrive (documented clear deviation from a previous growth trajectory in the last 3 months or Z score weight/age < 2)
 - o Failure of broad-spectrum antibiotics for treatment of pneumonia
 - Suggestive CXR features

OR

- History of contact with a TB case and any of the symptoms listed under point 2 with a shorter duration (< 2 weeks) if the child is HIV infected or present a SAM.
- One positive Xpert (MTB/Rif or Ultra) result from at least one respiratory sample: sputum or GA .

- Signed informed consent by parent or guardian and assent signed by children > 7 years old.

Non-inclusion criteria: Antituberculosis treatment > 5 days in the last 3 months, History of tuberculosis preventive treatment in the last 3 months, confirmed extrapulmonary TB only.

Trial agenda:

- First enrolment: January 2020
- End of prospective cohort enrolment: January 2021
- Interim-analysis: April 2021
- Start of enrichment cohort enrolment: January 2021
- · End of enrichment cohort enrolment: December 2021
- End of follow-up: February 2022
- Analysis-report: May 2022

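### Composite-reference sensitivity has no cohort restriction, so if both stages are pooled it is strongly driven by the 97-child enrichment quota

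*Protocol*

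**What the plan says.** **Enrolment.** Stage 1 takes consecutive children with presumptive TB: "we will need to enrol a total of 177 children with presumptive TB" (section 4.3). In stage 2, "only children with presumptive TB who are Xpert positive on at least one respiratory sample will be proposed to participate" (section 4.2), and the target is stated as "We will therefore a total of enrol 97 children with Xpert Ultra positive results during the second stage" (section 4.3). Appendix 1 gives the total: "Sample size: 274 children (below 15 years old".

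**Composite reference.** Section 2.2 counts confirmed plus unconfirmed TB as disease. Table 2 in section 3.3 defines confirmed TB as "Bacteriological confirmation obtained (Mycobacterium tuberculosis confirmed by culture or Xpert MTB/RIF assay from at least 1 respiratory specimen". The text below the table adds that a culture-negative child with a positive respiratory Ultra is negative for the primary endpoint but confirmed for the composite analysis.

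**Analysis.** Section 11.2.2 lists the "Head to head comparison of the sensitivities and specificities between the different stool processing methods using the TB composite reference standard", using McNemar tests, and names no cohort. Section 4.1 puts the secondary endpoints in the final analysis at the end of the study. Section 11.2.1 sets the primary analysis at "Patient level (denominator total number of cases with at least one stool sample collected", again without a cohort.

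**Specificity.** Section 4.1 is explicit that "this evaluation will be done among consecutively enrolled children with presumptive TB only". Section 11.2 does not repeat this.

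**The concern.** Under Table 2 every enrichment child is composite-positive because of how the child was selected, and none can be unconfirmed or unlikely TB. Those two groups come from stage 1 alone. If both stages are analysed together, composite sensitivity is a weighted average of stool positivity in confirmed and unconfirmed cases, and much of the weight is the number of Xpert-positive children the study chose to recruit.

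The composite analysis is meant to show performance beyond culture-confirmed disease, which largely means unconfirmed TB. A pooled figure would mostly reflect confirmed cases and would look far better than what applies to the population named in the primary objective, children with presumptive TB. The caveat in section 4.1 does not cover this: it warns of higher bacterial load among culture-confirmed children, not of an altered mix of confirmed and unconfirmed cases. Because the study is meant to inform WHO recommendations (section 4.1), the absolute figure is likely to be quoted.

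**Working it through.** **The plan's own sample size reproduces**, using n = 1.96² × p(1−p)/d².
- Specificity: 1.96² × 0.9 × 0.1/0.05² = 138.3, so 139 (stated 140). Then 140 × 1.15 = 161 (stated 160) and 160/0.90 = 177.8 (stated 177).
- Sensitivity: 1.96² × 0.6 × 0.4/0.10² = 92.2, so 93. Then 93/0.90 = 103.3 (stated 103), 103 − 16 = 87 and 87/0.90 = 96.7, so 97.
- Total: 177 + 97 = 274.

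**Inputs for composite sensitivity.**
- From the protocol: 177 and 97 children; 10% culture-confirmed in stage 1 (17.7 children); 60% stool positivity in confirmed cases.
- Assumed, because the protocol gives no figure: 20% to 50% of stage-1 children unconfirmed; 5% of them stool-positive; 70% of enrichment children stool-positive.

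**Formulas.** With U unconfirmed children:
- Stage 1 = (0.60 × 17.7 + 0.05 × U)/(17.7 + U)
- Pooled = (0.60 × 17.7 + 0.05 × U + 0.70 × 97)/(17.7 + U + 97)

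| Unconfirmed share | U | Stage 1 | Pooled | Enrichment share of composite positives |
|---|---|---|---|---|
| 20% | 35.4 | 12.39/53.1 = 23.3% | 80.29/150.1 = 53.5% | 97/150.1 = 65% |
| 40% | 70.8 | 14.16/88.5 = 16.0% | 82.06/185.5 = 44.2% | 97/185.5 = 52% |
| 50% | 88.5 | 15.05/106.2 = 14.2% | 82.95/203.2 = 40.8% | 97/203.2 = 48% |

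**Sensitivity to the assumptions.**
- With 60% positivity in enrichment children instead of 70%, the 40% row gives (14.16 + 58.2)/185.5 = 39.0% pooled, still against 16.0%.
- Table 2 also counts Xpert-positive children as confirmed, so 10% may be low for stage 1. At 15%, the upper end of the range in section 4.1, confirmed cases number 26.55. The 40% row becomes (15.93 + 3.54)/97.35 = 20.0% in stage 1 and (19.47 + 67.9)/194.35 = 45.0% pooled.
- Wider ranges (10% to 50% unconfirmed, 0% to 10% of them stool-positive, 60% in all confirmed cases, 18 confirmed in stage 1) give 10% to 35% in stage 1 and 34% to 53% pooled.

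**Dependence on the quota alone.** Take 18 confirmed and 53 unconfirmed in stage 1, with 60% and 5% stool-positive, and Q enrichment children at 60%: (13.45 + 0.60 × Q)/(71 + Q). For Q = 0, 50, 97, 150 and 200 this is 18.9%, 35.9%, 42.6%, 46.8% and 49.2%. Nothing about the test changes along that series.

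**Other case-mix-dependent results.** At 40% unconfirmed, with 2% assumed stool-positive among the 88.5 unlikely cases, stool positivity is (14.16 + 1.77)/177 = 9.0% in stage 1 and (15.93 + 67.9)/274 = 30.6% pooled. Kappa depends on that prevalence; trace, semi-quantitative and relative-gain results depend on who is positive.

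**Composite specificity.** No enrichment child can be composite-negative, so its denominator is the same with or without pooling.

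**Culture specificity, only if the section 4.1 rule were not followed.** About 10% of 97, roughly 10 children, would be Xpert-positive and culture-negative. Adding 10 to 160 stage-1 negatives, with 40% to 80% of the 10 assumed stool-positive:
- 90% would become (144 + 6)/170 = 88.2% down to (144 + 2)/170 = 85.9%.
- 99% would become (158.4 + 6)/170 = 96.7% down to (158.4 + 2)/170 = 94.4%.

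**The case against.** Four points can be made for the plan.

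- **Pooling is inferred.** Section 11.2.2 names no population, and a separate statistical analysis plan is to be written (section 11.1). This is true. But the end-of-study timing and the unrestricted denominator both point to pooling, and nothing restricts any secondary endpoint to stage 1. An analysis that follows section 11.2 as written would pool.
- **The listed item is a paired comparison.** McNemar tests use within-child discordant pairs and stay valid whatever the mix. This stands. The mix distorts the absolute sensitivities and the size of the differences, not the validity of the tests. Section 4.1 also says that enrichment is informative on how the methods differ, and dropping enrichment children from every paired comparison would discard most stool-positive composite cases (about 14 in stage 1 against 82 pooled at 40% unconfirmed).
- **Stage-1 agreement is already planned.** Sections 4.1 and 11.2.3 provide an interim analysis of accuracy and agreement on the prospective cohort. That partly covers kappa, but not trace, semi-quantitative or relative-gain results.
- **The size rests on assumptions.** It does. The direction does not, provided stool positivity is higher in enrichment children than in stage-1 composite positives overall.

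A reader might also infer from the section 11.2.1 denominator that specificity is computed on all children. The documents do not support that: section 4.1 limits specificity to consecutively enrolled children, and the denominator wording can be read as fixing only the unit of analysis. What remains is that section 11.2.1 does not carry the rule.

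**Conclusion.** The concern holds for absolute composite sensitivity. If the cohorts are pooled, as the timing and denominators suggest, the estimate is about 41% to 53% where the stage-1 value is about 14% to 23%. This assumes 20% to 50% unconfirmed, 5% of them stool-positive, 60% in stage-1 confirmed cases and 70% in enrichment children. Pooled, the figure does not describe children with presumptive TB, and the protocol's caveat does not warn of it.

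It would go too far to say that the quota alone sets the result or that enrichment children swamp the rest. That depends on an unconfirmed count the protocol does not give, and at 50% unconfirmed the 97 are just under half of composite positives. Nor does the point extend to composite accuracy as a whole. Primary culture specificity is protected if section 4.1 is followed. Severity is moderate.

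**What to change.** - **Section 11.2.2, composite standard:** estimate absolute sensitivity in the prospective cohort only, and give stool positivity separately for confirmed and unconfirmed cases. Paired between-method comparisons may keep enrichment children if they are labelled as including them.
- **Section 11.2.2, other results:** report kappa, trace, semi-quantitative and relative-gain results by cohort, with the prospective cohort as the figure that applies to presumptive TB.
- **Section 11.2.1:** repeat the section 4.1 rule that specificity uses only consecutively enrolled stage-1 children, so that the roughly 10 Xpert-positive, culture-negative enrichment children are not counted as negatives.

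This changes wording only and needs no new data. The cost is precision for composite sensitivity. Using 1.96 × √(p(1−p)/n) with the values above, the half-width at 20% unconfirmed is 11.4 points in stage 1 (p = 0.233, n = 53.1) against 8.0 pooled (p = 0.535, n = 150.1). At 40% it is 7.6 against 7.1. At 50% the two are about equal (6.6 against 6.8), because the stage-1 proportion is lower.
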